### **15.2. Access to Source Data**

The site investigators and site staff will make all source data available to the DAIT/NIAID and authorized representatives of DAIT/NIAID, as well as to relevant health authorities. Authorized representatives as noted above are bound to maintain the strict confidentiality of medical and research information that may be linked to identified individuals.

## **16. Quality Assurance and Quality Control**

Each clinical site will perform internal quality management of study conduct, data, and biological specimen collection, documentation, and completion. An individualized quality management plan may be reviewed by the clinical monitor during review of institutional SOPs.

The eCRFs will be completed online via a web-based EDC system that has been validated and is compliant with Part 11 Title 21 of the CFR. Quality control (QC) procedures will be implemented beginning with the data entry system, and data QC checks that will be run on the database will be generated. Any missing data or data anomalies will be communicated to the site(s) for clarification/resolution. All elements of data entry (i.e., time, date, verbatim text, and the name of the

person performing the data entry) will be recorded in an electronic audit trail to allow all changes in the database to be monitored and maintained in accordance with federal regulations.

Following written Standard Operating Procedures (SOPs), the monitors will verify that the clinical trial is conducted and data are generated and biological specimens are collected, documented (recorded), and reported in compliance with the protocol, International Council for Harmonisation of Technical Requirements for Pharmaceuticals for Human Use (ICH) E6(R2) Good Clinical Practice: Integrated Addendum to ICH E6(R1), or FDA Guidance for Industry: E6(R2) Good Clinical Practice: Integrated Addendum to ICH E6(R1), and applicable regulatory requirements (e.g., Good Laboratory Practices [GLP], Good Manufacturing Practices [GMP]).

The investigational site will provide direct access to all trial related facilities, source data/documents, and reports for the purpose of monitoring and auditing by the sponsor, and inspection by local and regulatory authorities.

## 17. Protocol Deviations

### 17.1. Protocol Deviation Definitions

- **Protocol Deviation** – The investigators and site staff will conduct the study in accordance to the protocol; no deviations from the protocol are permitted. Any change, divergence, or departure from the study design or procedures constitutes a protocol deviation. As a result of any deviation, corrective actions will be developed by the site and implemented promptly.
- **Major Protocol Deviation (Protocol Violation)** - A Protocol Violation is a deviation from the IRB approved protocol that may affect the participants' rights, safety, or well-being and/or the completeness, accuracy, and reliability of the study data. In addition, protocol violations include willful or knowing breaches of human subject protection regulations, or policies, any action that is inconsistent with the NIH Human Research Protection Program's research, medical, and ethical principles, and a serious or continuing noncompliance with federal, state, local or institutional human subject protection regulations, policies, or procedures. Examples of Major Protocol Deviations are described in the MOP.
- **Non-Major Protocol Deviation** - A non-major protocol deviation is any change, divergence, or departure from the study design or procedures of a research protocol that does not have a major impact on the participants' rights, safety or well-being, or the completeness, accuracy, and reliability of the study data.

### 17.2. Reporting and Managing Protocol Deviations

The study site principal investigator has the responsibility to identify, document and report protocol deviations as directed by DAIT/NIAID. However, protocol deviations may also be identified during site monitoring visits or during other forms of study conduct review.

Upon determination that a protocol deviation has occurred, the study staff will: (a) notify the site principal investigator (PI), (b) notify the SACCC (as Sponsor designee), and (c) will complete a Protocol Deviation form. The protocol deviation form will document at minimum the date the deviation occurred, the date it was identified, a description of the event, whether the deviation resulted in an AE/SAE, PI signature, IRB report requirement, and documentation of a corrective action plan. DAIT/NIAID may request discussion with the site PI to determine the effect of the protocol deviation on the study participant and his/her further participation, the effect of the protocol deviation on the overall study, and corrective actions. The DAIT/NIAID Medical Monitor will make the decision as to whether each deviation is major or not.

The PI will sign the paper source Protocol Deviation, electronically sign Major Deviations in the EDC, and submit the deviation to the central IRB, and local IRB/IEC per IRB regulations. Major protocol deviations will be reported to the DSMB by the DAIT/NIAID Medical Monitor at the medical monitor's discretion.

## **18. Ethical Considerations and Compliance with Good Clinical Practice**

### **18.1. Statement of Compliance**

This clinical study will be conducted using good clinical practice (GCP), as delineated in *FDA Guidance for Industry: E6(R2) Good Clinical Practice: Integrated Addendum to ICH E6(R1)*, and according to the criteria specified in this study protocol. Before study initiation, the protocol and the informed consent documents will be reviewed and approved by the central IRB. Any amendments to the protocol or to the consent materials will also be approved by the central IRB before they are implemented.

### **18.2. Informed Consent Process**

The consent process will provide information about the study to a prospective participant and will allow adequate time for review and discussion prior to his/her decision. The principal investigator listed on the FDA 1572 or designee will review the consent and answer questions. The prospective participant will be told that being in the trial is voluntary and that he or she may withdraw from the study at any time, for any reason. The participant will read, sign, and date a consent form before undergoing any study procedures. Consent materials will be presented in the participant's primary language. A copy of the signed consent form will be given to the participant.

The consent process will be ongoing. The consent form will be revised when important new safety information is available, the protocol is amended, and/or new information becomes available that may affect participation in the study.

### **18.3. Privacy and Confidentiality**

A participant's privacy and confidentiality will be respected throughout the study. Each participant will be assigned a unique identification number, and these numbers rather than names will be used to collect, store, and report participant information. All biospecimens will be labeled with unique identification numbers. Site personnel will not transmit documents containing personal health identifiers (PHI) to the study sponsor or their representatives.

Data reported in medical journals or scientific meetings will be presented in aggregate for participants as a whole. No individual participant will be identified in any way.

## **19. Publication Policy**

DAIT/NIAID will be responsible for organizing publication activities related to the multisite aggregate data and will work with the investigators to define the manuscript/presentation development process, the number and order of authors, the publication/scientific meeting to which it will be submitted, and related issues. DAIT/NIAID has final approval authority over all such issues. Single site data may be published by the site investigator(s) after the primary publication, or if the multisite aggregate data has not been published 24 months after database lock.

The National Institutes of Health (NIH) Public Access Policy will apply to this study. [20]

## Appendix 1. CoFAR Grading Scale for Systemic Allergic Reactions Version 3.0

Grade 1	Grade 2	Grade 3	Grade 4	Grade 5
Reaction involving one of the following organ systems in which the symptoms are mild:	Reaction involving two or more of the following organ systems in which the symptoms are mild:	Reaction involving one or more of the following organ systems:	Life-threatening reaction involving one or more of the following organ systems with or without other symptoms listed in Grades 1 to 3:	
Cutaneous Generalized pruritus, generalized urticaria, flushing, angioedema	Cutaneous Generalized pruritus, generalized urticaria, flushing, angioedema	Lower respiratory Throat tightness, wheezing, chest tightness, dyspnea, cough that respond to short-acting bronchodilator treatment (including IM epinephrine) with or without supplemental oxygen	Lower respiratory Throat tightness with stridor, wheezing, chest tightness, dyspnea, or cough associated with a requirement for supplemental oxygen and refractoriness to short-acting bronchodilator treatment (including IM epinephrine) 	
Upper respiratory Rhinitis, cough unrelated to laryngeal edema or bronchospasm	Upper respiratory Rhinitis, cough unrelated to laryngeal edema or bronchospasm			
Conjunctival Injection/redness, itching, tearing	Conjunctival Injection/redness, itching, tearing	GI Severe abdominal pain, more than two episodes of vomiting and/or diarrhea	OR  Respiratory compromise requiring mechanical support	
GI Nausea, abdominal pain (no change in activity level), single episode of vomiting and/or single episode of diarrhea	GI Nausea, abdominal pain (no change in activity level), single episode of vomiting, and/or single episode of diarrhea		Cardiovascular Reduced BP with associated symptoms of end-organ dysfunction (e.g., hypotonia [collapse], syncope) defined as: 
 
• Children: low systolic BP (age specific) or >30% decrease in systolic BP
 
• Adults: systolic BP of less than 90 mmHg or >30% decrease from baseline
 
	
	OR  Reaction involving at least one of the following organ systems in which the symptoms are moderate:			
	Cutaneous Generalized pruritus, generalized urticaria, flushing, angioedema			
	Upper respiratory Rhinitis, cough unrelated to laryngeal edema or bronchospasm			
	Conjunctival Injection/redness, itching, tearing			
	GI Nausea, abdominal pain (with change in activity level), two episodes of vomiting and/or diarrhea			

1. Examples of refractoriness could include continuous albuterol nebulizer or epinephrine IV infusion or more than three IM epinephrine injections.

2. Low systolic BP for children is defined as: less than 70 mmHg from 1 month to 1 year of age, less than (70 mmHg + [2 x age]) from 1 to 10 years of age, and less than 90 mmHg from 11 to 17 years of age.

## Appendix 2: Brighton Collaboration Criteria

### Case Definition of Anaphylaxis

For all levels of diagnostic certainty	Level 1 of diagnostic certainty	Level 2 of diagnostic certainty	Level 3 of diagnostic certainty

Anaphylaxis is a clinical syndrome characterized by
 
 
• sudden onset AND
 
• rapid progression of signs and symptoms AND
 
• involving multiple (<math>\geq 2</math>) organ systems, as follows →
 
	
• <math>\geq 1</math> major dermatological AND
 
• <math>\geq 1</math> major cardiovascular AND/OR
 
<math>\geq 1</math> major respiratory criterion
	
• <math>\geq 1</math> major cardiovascular AND <math>\geq 1</math> major respiratory criterion
 
OR
 
• <math>\geq 1</math> major cardiovascular OR respiratory criterion AND
 
• <math>\geq 1</math> minor criterion involving <math>\geq 1</math> different system (other than cardiovascular or respiratory systems) OR
 
• (<math>\geq 1</math> major dermatologic) AND (<math>\geq 1</math> minor cardiovascular AND/OR minor respiratory criterion)
	
• <math>\geq 1</math> minor cardiovascular OR respiratory criterion AND
 
• <math>\geq 1</math> minor criterion from each of <math>\geq 2</math> different systems/categories

The case definition should be applied when there is no clear alternative diagnosis for the reported event to account for the combination of symptoms.

### Major and minor criteria used in the case definition of anaphylaxis

	Major Criteria	Minor Criteria
Dermatologic or mucosal	
 
• generalized urticaria (hives) or generalized erythema
 
• angioedema*, localized or generalized
 
• generalized pruritus with skin rash
 
	
 
• generalized pruritus without skin rash
 
• generalized prickle sensation
 
• localized injection site urticaria
 
• red and itchy eyes
 

Cardiovascular	
 
• measured hypotension
 
• clinical diagnosis of uncompensated shock, indicated by the combination of at least 3 of the following: 
 
• tachycardia
 
• capillary refill time <math>>3</math> s
 
• reduced central pulse volume
 
• decreased level of consciousness or loss of consciousness
 
 
 
	
 
• reduced peripheral circulation as indicated by the combination of at least 2 of 
 
• tachycardia and
 
• a capillary refill time of <math>>3</math> s without hypotension
 
• a decreased level of consciousness
 
 
 

Respiratory	
 
• bilateral wheeze (bronchospasm)
 
• stridor
 
• upper airway swelling (lip, tongue, throat, uvula, or larynx)
 
• respiratory distress—2 or more of the following: 
 
• tachypnoea
 
• increased use of accessory respiratory muscles (sternocleidomastoid, intercostals, etc.)
 
• recession
 
• cyanosis
 
• grunting
 
 
 
	
 
• persistent dry cough
 
• hoarse voice
 
• difficulty breathing without wheeze or stridor
 
• sensation of throat closure
 
• sneezing, rhinorrhea
 

Gastrointestinal		
 
• diarrhoea
 
• abdominal pain
 
• nausea
 
• vomiting
 

Laboratory		Mast cell tryptase elevation $>$ upper normal limit

\* Not hereditary angioedema

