### 3. Study Design

#### 3.1. Description of Study Design

This is a multi-center, randomized, initially blinded, phase 2 trial to assess SARS-CoV-2 vaccination reactions in two populations: one population including individuals with a history of recent, severe allergic reactions, poorly controlled allergic asthma, or MCDs and one comparison population without severe allergies or mast cell disorders. The study aims at enrolling up to 2040 HA/MCD and 1360 comparison participants across approximately 30 US sites.

Approximately two-thirds of participants enrolled in each of the 2 groups will be female. This is because the vast majority of cases of anaphylaxis to the COVID-19 vaccines have occurred in women. Enrollment of participants who qualify only on the basis of reactions to multiple unrelated drugs will be limited to approximately 300. Enrollment of the MCD group is anticipated to be at least 200 participants, and not more than 300 participants.

Participants enrolled under protocol versions 1.0 – 4.0 were randomized 2:2:1:1 to receive the Pfizer-BioNTech COVID-19 Vaccine, Moderna COVID-19 Vaccine, placebo + Pfizer-BioNTech COVID-19 Vaccine, or placebo + Moderna COVID-19 Vaccine (Figure 1).

Participants enrolled under protocol versions 5.0 – 8.0 will be randomized 2:1 to receive the Pfizer-BioNTech COVID-19 Vaccine or placebo + Pfizer-BioNTech COVID-19 Vaccine. If enrollment is robust and sustained, active vaccine randomization may be changed to Moderna.

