#### High-Allergy and Mast Cell Disorder (HA/MCD) group:

Individuals who meet at least one of the following criteria are eligible for enrollment in the HA/MCD group:

1. History of a severe allergic reaction to food(s), allergen immunotherapy, insect venom(s), or latex with use of epinephrine within the last 15 years
2. History of an Emergency Department visit with convincing evidence of a systemic allergic reaction (consistent with CoFAR Grade 3 or higher) to food(s), allergen immunotherapy, insect venom(s), or latex within the last 15 years
3. History of documented, immediate allergic reactions to 2 or more unrelated drugs within the last 15 years
4. A convincing clinical history, or a history that is accompanied by a positive skin test, of an immediate reaction to a drug, vaccine, or latex within the last 15 years
5. History of physician-diagnosed idiopathic anaphylaxis with use of epinephrine or an Emergency Department visit within the last 15 years
6. History of a physician-diagnosed mast cell disorder (e.g., mastocytosis, mast cell activation syndrome (MCAS), or hereditary alpha-tryptasemia). MCAS must meet consensus criteria[17], as defined below:
  - Criterion A: Typical clinical signs of severe, recurrent (episodic) systemic MCA are present (often in form of anaphylaxis) (definition of systemic: involving at least 2 organ systems)
  - Criterion B: Involvement of MC is documented by biochemical studies: preferred marker: increase in serum tryptase level from the individual's baseline to plus 20% + 2 ng/ml
  - Criterion C: Response of symptoms to therapy with MC-stabilizing agents, drugs directed against MC mediator production or drugs blocking mediator release or effects of MC-derived mediators

All 3 MCAS criteria (A + B + C) must be fulfilled to call a condition MCAS.

7. Poorly controlled asthma as evidenced by one hospitalization or one or more systemic (oral or injectable) steroid burst(s) in the 24 months prior to enrollment and evidence of aeroallergen sensitization by blood work, skin test, or appropriate history.
8. A doctor diagnosis of food allergy with a convincing clinical history and a positive skin test or positive food challenge, with evidence of reactivity in the last 10 years.

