#### Comparison group:

Individuals who meet all of the following criteria are eligible for enrollment in the comparison group:

1. No history of allergic asthma or atopic dermatitis within the last 10 years
2. No history of chronic spontaneous urticaria or angioedema
3. No history of allergic reactions to foods or insect venoms
4. No history of allergic reactions to drugs or vaccines
5. No history of anaphylaxis
6. No history of a mast cell disorder (e.g., mastocytosis, MCAS, or hereditary alpha-tryptasemia)

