7.3. Secondary Endpoints

All secondary endpoints will be analyzed for participants enrolled under version 1.0 through 4.0. If sufficient numbers of children are enrolled, then adults 18 years of age and older will be also be analyzed separately from children.

7.3.1. Secondary Endpoint 1

Endpoint: The proportion of participants who experience a severe (Grade 3 or higher per [CoFAR Grading Scale for Systemic Allergic Reactions Version 3.0](#)) systemic allergic reactions within the 90-minute post-vaccination observation period to either dose of each vaccine.

Computation: A Grade 3 or higher systemic allergic reaction, categorized as yes or no, is defined as a participant having a Grade 3 or higher (per CoFAR Grading Scale V3.0) systemic allergic reaction to either active dose 1 or active dose 2 (categorized as yes) or to neither active dose (categorized as no).

Participants who do not have a systemic allergic reaction to the 1st active dose but missing data for their 2nd active dose will be removed from this analysis (complete case analysis).

Analysis: This analysis will be carried out as outlined in Section 7.2.2. A sensitivity analysis will be carried out as outlined in Section 7.2.3.

7.3.2. Secondary Endpoint 2

Endpoint: The proportion of participants who experience an anaphylactic reaction (Levels 1-3) per Brighton Collaboration Criteria within the 90-minute post-vaccination observation period to either dose of each vaccine.

Computation: An anaphylactic reaction (Levels 1-3) per Brighton Collaboration Criteria, categorized as yes or no, is defined as a participant having an anaphylactic reaction (Levels 1-3) per Brighton Collaboration Criteria to either active dose 1 or active dose 2 (categorized as yes) or to neither active dose (categorized as no).

Participants who do not have a systemic allergic reaction to the 1st active dose but missing data for their 2nd active dose will be removed from this analysis (complete case analysis).

Analysis: This analysis will be carried out as outlined in Section 7.2.2. A sensitivity analysis will be carried out as outlined in Section 7.2.3.

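### The Brighton anaphylaxis endpoint reads tryptase against a fixed limit rather than the participant's own baseline, which can bias the HA/MCD-versus-comparison contrast upward

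*Protocol*

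**What the plan says.** **Endpoint.** SAP 7.3.2 codes secondary endpoint 2 as yes or no. It "is defined as a participant having an anaphylactic reaction (Levels 1-3) per Brighton Collaboration Criteria to either active dose 1 or active dose 2". It adds no rule for tryptase, then sends the endpoint to the between-cohort analysis of SAP 7.2.2 (Barnard's test). Protocol 14.4.3 plans only estimates with exact confidence intervals for this endpoint and rules out inference because events should be very rare. SAP section 11 does not list the added test as a change from the protocol.

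**Definition.** In Protocol Appendix 2 the laboratory minor criterion is "Mast cell tryptase elevation $>$ upper normal limit". Level 3 needs one minor cardiovascular or respiratory criterion, plus minor criteria from each of at least two "different systems/categories". Every level also requires sudden onset, "rapid progression of signs and symptoms AND" at least two organ systems. A closing note adds: "The case definition should be applied when there is no clear alternative diagnosis for the reported event to account for the combination of symptoms".

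**Populations.** HA/MCD criterion 6 in Protocol 4.2 admits "History of a physician-diagnosed mast cell disorder (e.g., mastocytosis, mast cell activation syndrome (MCAS), or hereditary alpha-tryptasemia", with no cap on resting tryptase. The comparison group requires "No history of a mast cell disorder (e.g., mastocytosis, MCAS, or hereditary alpha-tryptasemia". Protocol 3.1 states: "Enrollment of the MCD group is anticipated to be at least 200 participants, and not more than 300 participants".

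**Tryptase elsewhere.** The primary endpoint accepts a CoFAR Grade 1 reaction only if tryptase reaches 1.2 x baseline + 2 ng/ml. SAP 7.2.1 also says who decides when a tryptase value is missing. SAP 7.3.2 has neither rule.

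**The concern.** A criterion meant to describe the reaction can be met by a value that was there before the injection. If that happens more often in one cohort than in the other, the same symptoms are classed differently by cohort, and the difference in Brighton proportions partly reflects the entry diagnosis. The trial already reads tryptase against the individual's baseline in its primary endpoint and in MCAS Criterion B, so one blood result would be judged by two different standards.

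Protocol 1.1 includes Brighton to allow comparison with published rates, and the unmodified definition serves that purpose. The contrast between HA/MCD and comparison is a different use. There a cohort-dependent criterion matters, and more so if a p-value is attached.

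**Working it through.** **1. The plan's own figures.** The documents give no figure for the Brighton endpoint itself, but Protocol 14.7 uses the same estimator. For 0/1020 the exact upper limit is 1 − 0.025^(1/1020) = 0.0036, as stated. For 10/1020 the exact interval is (0.0047, 0.0180), stated as (0.005, 0.018). The exact unconditional score test with doubled one-sided p-value, at 1,020 versus 680 and 0.01 versus 0.0001, has power 85.3%, consistent with the stated minimum of 80%.

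**2. What the Level 3 rule does once the laboratory category is already met.** Take the four clinical categories, minor criteria only.

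| Minor criteria present | Level 3 without laboratory | Level 3 with laboratory |
|---|---|---|
| Respiratory + gastrointestinal | no | yes |
| Cardiovascular + gastrointestinal | no | yes |
| Cardiovascular + respiratory | no | yes |
| Dermatologic + respiratory | no | yes |
| Dermatologic + cardiovascular | no | yes |
| Dermatologic + gastrointestinal | no | no |

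Five of the six two-category combinations change. No single-category presentation changes. Any three of the four categories include a respiratory or cardiovascular one, so they are Level 3 already. The general conditions (sudden onset, rapid progression, no clear alternative diagnosis) apply in every row. I leave Level 2 aside, because its minor-criterion clause speaks of systems and does not mention categories.

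**3. Fixed limit against baseline-relative rule.** Let T0 be tryptase before injection and T1 after it. If T0 is above the limit and nothing changes, T1 = T0 and the Appendix 2 criterion is met. The rule T1 ≥ 1.2 x T0 + 2 needs a rise of at least 0.2 x T0 + 2, so T1 = T0 fails for every T0. None of the five rows then changes without a real rise.

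**4. Who is exposed.** The share of HA/MCD is 200/2040 = 9.8% to 300/2040 = 14.7%. That is about 100 to 150 per vaccine, assuming an even split and full planned enrolment. SAP 7.3 analyses versions 1.0 to 4.0, so the actual numbers may be smaller.

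**5. Possible size, by assumption.** Extra cases = n x f x q. Here n is the number with a mast cell disorder per vaccine, f the share of them with resting tryptase above the limit, and q the share of those with a qualifying two-category presentation after either dose. Neither f nor q is in the documents. I take f from 10% to 100% and q from 1% to 10%.

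- Low end: 100 x 0.10 x 0.01 = 0.1 case; 0.1/1020 = 0.01 percentage point.
- Middle: 100 x 0.50 x 0.05 = 2.5 cases; 2.5/1020 = 0.25 percentage point.
- High end: 150 x 1.00 x 0.10 = 15 cases; 15/1020 = 1.47 percentage points.

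**6. Sensitivity of the SAP test.** By the test in step 1, 6/1020 versus 0/680 gives p = 0.056 and 7/1020 versus 0/680 gives p = 0.038. Near that boundary one reclassified participant decides the result.

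**The case against.** The strongest objection is that the key input is missing. Neither document states an upper normal limit, a resting tryptase value, or the share of participants above the limit. A reader might infer that the admitted diagnoses imply raised resting tryptase. The documents do not say so, and their one tryptase rule for such a disorder, MCAS Criterion B, is a rise from the individual's baseline. This stands: the mechanism is in the text, its size is not.

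A reader might also infer that only HA/MCD can be affected. That goes too far. Comparison participants are screened by history and not by a tryptase measurement, so an unrecognised high resting value is possible, and anyone can meet the criterion through a true rise. Within HA/MCD, some 85% to 90% are outside the mast cell disorder group.

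Nor do any mild symptoms in two systems suffice. One must be a minor respiratory or cardiovascular criterion, and the general conditions still apply. These conditions narrow the problem, but none of them concerns resting tryptase.

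It is tempting to set one extra case in 1,020 against the published rates per million doses and infer a large inflation. Any single case, true or false, would give that result, and the comparison mixes a proportion of participants with a rate per dose.

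Finally, events are expected to be very rare, so a case resting on tryptase could be noticed on review. Without a rule fixed beforehand, however, that decision would be made after the case is known.

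**Conclusion.** The point holds, with moderate confidence, for secondary endpoint 2. As written, a pre-injection laboratory value can supply one of the categories needed for Level 3. This is possible mainly in the mast cell disorder part of HA/MCD, and the direction of the bias in the between-cohort contrast is upward. The magnitude is unknown; the range of 0.1 to 15 extra cases per 1,020 rests entirely on the assumed f and q and on 100 to 150 such participants per vaccine.

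A reader might infer that the primary result is also at risk. It is not. Its tryptase rule applies to Grade 1 only and is baseline-relative, and under Appendix 1 mild symptoms in two listed organ systems are Grade 2 in either cohort whatever the tryptase. No figure stated in the documents is wrong because of this point. The unmodified Brighton count also remains right for comparison with publications.

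**What to change.** In SAP 7.3.2:

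- Keep the unmodified Brighton Levels 1-3 count for comparison with publications.
- Pre-specify beside it, for the HA/MCD-versus-comparison contrast, a count in which the laboratory criterion is credited only when post-injection tryptase is above the upper normal limit and at least 1.2 x the pre-vaccination value + 2 ng/ml.
- Apply the missing-tryptase rule of SAP 7.2.1, under which the study management team decides from all available data.
- Show both counts by mast cell disorder status. Use inclusion criterion 6, since the randomisation stratum also contains idiopathic anaphylaxis.
- Reconcile the Barnard's test reached through SAP 7.2.2 with Protocol 14.4.3. Either drop the test or record it in SAP section 11 as a change.

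The cost is SAP wording and two Brighton counts to present. The second count is not standard Brighton and will not credit a genuine rise below the threshold, so it belongs beside the standard count and does not replace it. No new sample is needed: Protocol 10.1 draws tryptase before and after injection at every visit under versions 1.0 to 4.0, the versions SAP 7.3 analyses. If the count is extended to versions 5.0 to 8.0, Protocol 10.2 provides a pre-vaccination value at Visit 1 only, and the SAP should name it as the baseline.
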